9.3 POPULATIONS FOR ANALYSES

Our primary population for analysis of treatment effect (Aim 3) will be the Intention-to-Treat (ITT) Analysis Population (i.e., all randomized participants). We will also conduct Per-Protocol analyses on the subset considered to have completed the intervention (at least 4 treatment sessions).

9.4 STATISTICAL ANALYSES

Aim 1: Examine the feasibility of the MC approach within an RCT.

- H1: Study recruitment will be 4 participants/month, retention in both treatment groups will be $\geq 85\%$, and $\geq 85\%$ of participants in both groups will complete the intervention in 12 weeks.

We will track and report recruitment, retention, intervention duration, and reasons for non-enrollment or attrition throughout the study period. Based on our preliminary study, we anticipate no problems in meeting our hypothesized thresholds. We enrolled 3 participants/month (with only 1 treating therapist and without an existing cohort from which to recruit), had 87.5% retention, and 85.7% of participants completed the intervention in the allotted timeframe⁵³. With N=60, if we meet our retention and completion goals (85%), we can be 95% certain of true rates of at least 73% (see Table in Section 9.2).

Aim 2: Demonstrate adequate treatment fidelity to the MC approach.

- H2a: Therapists will deliver MC with good adherence ($\geq 80\%$) and proficiency (scores $\geq 2/3$).

Blinded raters will rate therapist adherence and proficiency for a random sample (30%, n=180) of MC and Control treatment sessions. We will calculate adherence and proficiency (to MC) for each therapist; adherence $\geq 80\%$ and proficiency ≥ 2 (out of 3, indicating at least “Adequate”) will be benchmarks for good treatment integrity.

- H2b: MC participants will have good acceptance (CSQ-8 $\geq 24/32$, indicating all positive responses), receipt (PRPS $\geq 4/6$, indicating at least “Good”) and enactment (homework completion $\geq 80\%$).

MC participants will complete the Client Satisfaction Questionnaire (CSQ-8) at post-treatment, and blinded raters will rate participants’ session participation (Pittsburgh Rehabilitation Participation Scale; PRPS) and homework completion. CSQ-8 scores ≥ 24 , PRPS scores ≥ 4 , and homework completion rates $\geq 80\%$ will be benchmarks for good acceptance, receipt, and enactment, respectively.

For the Aim 2 outcomes, we will calculate mean scores $\pm 95\%$ confidence bounds (CBs) and compare them to our stated thresholds. To assess treatment differentiation, we will compare Proficiency scores for the MC and Control sessions using *t*-tests. We can also categorize participants using cutoffs (e.g., homework: <50% = Poor, 50-79% = Fair, $\geq 80\%$ = Good) for descriptive purposes and compare the MC and Control groups’ scores on outcomes using appropriate non-parametric tests.

Aim 3: Obtain preliminary estimates of the MC approach's effect on patient-reported functional cognition.

- H3 (exploratory): MC participants will report greater improvement in functional cognition than Control participants immediately and 3 months after treatment.

We will compare treatment effects (Goal Attainment) using mixed model repeated measures ANOVA (2: group X 3: time point). We chose this model because we want to use statistical contrasts to compare pre-post and pre-follow up changes across group. We will evaluate the pattern of correlations within subjects and test various correlation structures as appropriate using Akaike's information criteria and the Schwarz Bayesian criteria. However, our purpose is not to demonstrate efficacy, but rather to obtain effect size data to inform sample size calculations for a definitive RCT. To this end, we will generate mean change between the time points with 95% CIs. We will compare these data to the suggested minimally clinically important difference (≥ 2 points improvement)⁸⁹ to help determine the appropriate sample size to test the hypothesis that, in addition to being superior to the Control treatment, MC produces a clinically significant effect⁹⁰. We will also create a sample size table for various effect size values due to uncertainty of pilot estimates⁹¹.

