
missed opportunities) along with their evaluation of strategy effectiveness and potential modifications on a structured worksheet, which is reviewed collaboratively in the next session. In this way, homework not only supports real-life strategy application and practice, but it also reinforces self-monitoring, self-evaluation, problem solving, strategy self-generation, and strategy optimization. Treatment progresses through three general phases (1: Understand and define problems and goals, 2: Generate, execute, and evaluate strategies, 3: Generalize and reinforce strategy use) and increases in difficulty, but progression is flexible depending on the client's goals and abilities.

Control:

This treatment parallels the cognitive process training used in PD to-date but with simulated functional tasks (vs. computer or paper & pencil tasks). It has the same basic protocol as MC, but it is therapist-directed, and the OT does not address strategies, metacognition, generalization, or use mediation or action plans. Therefore, this is a standard-of-care approach that includes all but the proposed critical elements of MC. The OT reviews pre-treatment cognitive test scores with the client but without discussion to build awareness. The OT selects treatment activities based on the client's cognitive profile and goals from a published set of activities designed for use in cognitive interventions⁷³. Graded task practice with OT feedback on performance accuracy is used to produce neurocognitive improvement (or possibly independent strategy development). The OT assigns practice of specific cognitively challenging everyday life activities for homework (but without action plans).

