6.1.2 ADMINISTRATION AND/OR DOSING

Both interventions consist of 10 1-1.5 hour sessions over 12 weeks delivered in an individual, face-to-face format in participants' homes and/or communities by trained licensed occupational therapists (OTs). Care partners are also invited to participate.

A complete intervention is defined as completion of 10 OT sessions.

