6.2 FIDELITY

6.2.1 INTERVENTIONIST TRAINING AND TRACKING

Training: MC training will consist of a 2-day PI and Co-I led workshop and regular meetings. Control training will consist of a 1-day PI led workshop and regular meetings. Both will involve reading, didactic instruction, interactive discussions and activities, role-playing, and videotaped examples. Each therapist will observe the PI conduct treatment with 1 participant and then will conduct treatment with 1-2 participants under PI supervision. The Co-I has extensive experience training and supervising OTs in the MC Approach^{49,74,75}, and the PI has extensive experience administering it. The study OTs will have requisite knowledge in metacognitive strategy training and task-oriented training and clinical experience with PD.

Supervision: We will audiotape all treatment sessions, and the PI and Co-I will review the tapes and meet with the therapists to reinforce training, correct problems, and discuss issues. Initially, 50% of the tapes

will be reviewed, and the teams will have weekly meetings; this will reduce to 20% review and fewer meetings when appropriate⁵⁶.

Assessment: Interventionist fidelity is a primary outcome of this study (Aim 2a) and thus will be formally assessed. *See section 8.1.*

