8 STUDY ASSESSMENTS AND PROCEDURES

8.1 ENDPOINT AND OTHER NON-SAFETY ASSESSMENTS

A trained tester blind to treatment group will conduct Pre and Post testing while participants are on their regular medication (to prevent motor interference⁶³ and best represent their function in daily life). Testing will occur at the same time of day to control for potential effects of dosage timing or wearing off. Follow-up assessment will occur via web-based or mailed survey.

Primary outcomes:

Aim 2

- Therapist fidelity: Trained raters who are blind to study purpose and treatment group will use the *MC Fidelity Tool* to perform the following ratings. *Adherence*: Proportion of protocol steps that occurred within the session will be rated as present or absent. *Proficiency*: Quality of delivery of each of MC's critical treatment components will be rated on a 4-point scale (0=Did not occur, 1=Little Evidence/Inadequate, 2=Emerging/Adequate, 3=Proficient; averaged for a competence score) with detailed guidelines for each component and anchor. The raters will rate a random sample (30%, n = 180) of MC and Control session audiofiles (evenly distributed across condition, OT, treatment session number, and study month).
- Acceptance: We will administer the *Client Satisfaction Questionnaire* (CSQ-8)^{76,77} at post-treatment via mailed or web-based survey. Items have 4-point response scales (3-4: positive, 2: neutral, 1: negative) and are summed for a total score; higher scores indicate higher acceptance.
- Receipt: The raters will rate participants' engagement in treatment sessions with the *Pittsburgh Rehabilitation Participation Scale* (PRPS)⁷⁸ from the audiofiles (3 sessions per participant). The PRPS is a 6-point scale (1=None, 6=Excellent) with full descriptions of each anchor. Session scores are averaged for a single score, which is reliable and predictive of rehabilitation outcomes^{78,79}.
- Enactment (i.e. Adherence): The raters will code homework completion for each session (0=Did not do, 0.5=Partial, 1=Complete). We will sum these scores and divide by the total number of homework assignments (10) to yield a homework completion rate for each participant.

Aim 3

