10.2 PROTOCOL AMENDMENT HISTORY

*The table below is intended to capture changes of versions of the protocol, including a description of the change and rationale. A **Summary of Changes** table for the current amendment is located in the **Protocol Title Page**.*

Version	Date	Description of Change	Brief Rationale
2	May 2020	Changed randomization process and related communication among team members	To remove PI from randomization process and blind her to study group; minimize bias
2	May 2020	All participants will undergo 10 treatment sessions	To ensure treatment groups are balanced on dose of intervention
2	May 2020	Changed definition of screen failure from what was initially provided by this template	Study monitor request
2	May 2020	Added criteria used to declare failure for each aim to Objectives and Endpoints section	To enhance rigor and inform decision-making for next steps
2	May 2020	Specified target interval limits for timing of assessment and treatment sessions (see Schema)	To enhance rigor
2	May 2020	Added question to AE report form to monitor for psychological risks	A stated risk of the study, needed to capture it
2	May 2020	Added a question to the Follow-up assessment to monitor for perceived confidentiality breach	A stated risk of the study, needed to capture it
3	Nov 2020	Fixed Schedule of Activities table to indicate that inclusion/exclusion criteria are assessed in Visit 1 (via MoCA); consent form will also be modified to include this information	To fix a prior inconsistency pointed out by study monitor
4	Dec 2020	Added phone/blind MoCA to screening phone call	To reduce risk of enrolling people who do not meet cognitive criteria for entry
4	Dec 2020	Specified randomization ratio changes over course of study	To enhance transparency
5	May 2021	Added note that participants excluded post-randomization count as failures in retention endpoints	To enhance rigor and transparency

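### MC fidelity benchmarks and their precision should rest on MC sessions only, and Control delivery and session minutes should be described by arm

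*Combined protocol and SAP*

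**What the plan says.** **Instrument and sample.** Section 8.1 names the MC Fidelity Tool as the means of rating therapists. On sampling: "The raters will rate a random sample (30%, n = 180) of MC and Control session audiofiles", to be "evenly distributed across condition, OT, treatment session number, and study month". Adherence is the share of protocol steps rated present. On proficiency: "Quality of delivery of each of MC's critical treatment components will be rated on a 4-point scale", from 0 (did not occur) to 3 (proficient).

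**Analysis.** Section 9.4: "We will calculate adherence and proficiency (to MC) for each therapist". The benchmarks of 80% and 2 follow in the same sentence and are called good treatment integrity. Proficiency in MC and Control sessions is to be compared by t-test to show treatment differentiation. The failure criteria in Section 3 (average adherence of 75% or less, average competence below 2) name no arm. The Section 9.2 table gives adherence bounds of 78 to 82% around 80%, with n=153.

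**Control.** Section 6.1.1 gives Control the same basic protocol as MC but leaves out strategies, metacognition, generalization, mediation and action plans. Its own working element is stated: "Graded task practice with OT feedback on performance accuracy is used to produce neurocognitive improvement". The therapist also selects activities from a published set and assigns everyday practice at home.

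**Contact.** Section 6.1.2: "Both interventions consist of 10 1-1.5 hour sessions over 12 weeks". The amendment history (Section 10.2) explains the move to 10 sessions for everyone: "To ensure treatment groups are balanced on dose of intervention". Section 6.2.1 says all sessions are audiotaped. Section 9.4 tracks intervention duration, with completion within 12 weeks as the target. No section mentions minutes per session by arm.

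**The concern.** Aim 2 asks whether MC was delivered as intended, and H2a is worded about MC. Yet the analysis sentence covers every therapist, and the stated precision counts sessions from both arms. Section 6.3 notifies therapists of assignments to their own group, which suggests that each therapist serves one arm. Read literally, the 80% and 2/3 benchmarks would then be applied to therapists whose job is to leave MC's components out.

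The second gap is on the comparator. Control is built to hold everything in MC except the ingredients thought to matter, so that a difference in Goal Attainment can be credited to those ingredients. That reasoning needs some evidence that Control's own content was delivered and that contact was similar. The plan sets no rating, benchmark or failure criterion for Control content and no comparison of minutes. What is at stake is how the exploratory Aim 3 between-group estimate is read when it informs the definitive trial.

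**Working it through.** **1. Reproduce the plan's counts.** Sections 8.1 and 9.2 give 60 participants, 10 sessions, 30% sampled and 15% attrition.
- 60 × 10 × 0.30 = 180 sessions, as stated.
- 180 × 0.85 = 153 observations, as stated.

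The 180 cover MC and Control, so the 153 pool both arms.

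**2. MC sessions only.** Sampling is even by condition.
- 180 / 2 = 90 MC sessions.
- 153 / 2 = 76.5, so about 76 after attrition.

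**3. Adherence bounds.** The stated half-width is 2 points with n=153.
- Implied SD = 2 × √153 / 1.96 = 12.6 points.
- n=90: 1.96 × 12.6 / √90 = ±2.6 points.
- n=76: 1.96 × 12.6 / √76 = ±2.8 points, or ±2.9 with the t quantile.
- The stated bounds are rounded. A true half-width of 1.5 to 2.5 points gives ±2.2 to ±3.6 points at n=76.

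Proficiency behaves the same way. A half-width of 0.1 at n=153 implies an SD of 0.63, and ±0.14 at n=76. These figures ignore clustering of sessions within therapist and participant.

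**4. What pooling would do to proficiency.** With equal halves, the pooled mean is (MC mean + Control mean) / 2. As a limiting illustration, suppose Control contains no MC component and scores 0. MC at the benchmark of 2 then gives (2 + 0) / 2 = 1.0, and MC at the scale maximum gives (3 + 0) / 2 = 1.5. Both fall below the Section 3 failure line of 2. Real Control scores may be above 0, but low scores are what the design intends.

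**5. What the differentiation t-test can show.**

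| Control delivery | Expected MC proficiency in Control | Reading by the t-test |
|---|---|---|
| Delivered well, no MC content | Low | Arms differentiated |
| Delivered poorly, no MC content | Low | Arms differentiated |
| Contaminated with MC content | Higher | Arms less differentiated |

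The test detects contamination. It gives the same answer in the first two rows.

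**6. Contact time.** 10 × 1 h = 10 h and 10 × 1.5 h = 15 h per completer. This is the range the rules permit in either arm, not an expected difference between arms.

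The precision of a comparison needs an SD that the documents do not give. Assume a between-participant SD of 5 to 15 minutes in mean session length. The 95% half-width for the arm difference is t × SD × √(2/n):
- 30 per arm: 2.6 to 7.8 minutes.
- 25 per arm: 2.8 to 8.5 minutes.

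Under that assumption, the existing recordings can show a material difference or make one unlikely.

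**The case against.** The case for leaving the plan alone has several sound parts.

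- Aim 2 and H2a are about MC, so in context the benchmarks probably already mean MC delivery. That stands as a reading of intent. It does not cure the wording of Section 9.4 or a precision figure that counts both arms.
- Adherence is defined by protocol steps, and Control shares the basic protocol, so some items may be scored meaningfully on Control tapes. The tool's items are not in the documents, so a reader who infers that Control tapes yield no information on Control delivery goes too far. The specified between-arm test, however, uses proficiency.
- Control therapists are not left alone. Section 6.2.1 has each therapist observe a case and treat 1 to 2 participants under supervision, with 50% and later 20% of tapes reviewed. Participation ratings, homework and credibility are collected without restriction by arm, and Section 9.4 allows optional group comparisons. These are real but indirect safeguards. Supervision is not an endpoint, and the participant measures do not rate what the therapist did.
- On preparation: "Control training will consist of a 1-day PI led workshop and regular meetings", against 2 days for MC. A reader might infer an under-trained comparator. MC has more content to teach, so the difference does not show that.
- A reader might infer that one arm could get 50% more therapist time (15 h against 10 h). That needs every session at the maximum in one arm and at the minimum in the other. Nothing in the documents predicts it.
- Aim 3 is exploratory, efficacy is disclaimed, and Section 9.4 promises a sample size table over several effect sizes. This limits the consequence. The table addresses uncertainty in the estimate, though, and cannot show whether the comparator was well delivered.

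**Conclusion.** The point holds as a gap in specification and measurement. The benchmarks and bounds for MC fidelity are not limited to MC sessions. On MC sessions alone, the adherence half-width is about 2.8 to 2.9 points rather than 2. This assumes an even split by condition, 15% attrition in each arm and the SD implied by the plan's own table. Pooling would lower mean proficiency, possibly below the failure line. The documents do not say that the averages will be pooled, only that nothing prevents it.

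Control delivery is evidenced only indirectly, and session minutes are not compared. A reader might conclude that a weak or shorter Control could never be told from a true MC effect, or that the Aim 3 estimate will be inflated. The documents support neither. The limitation lies in the specified analyses, every session is recorded, and no figure in the plan gives the direction or size of any bias.

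**What to change.** 1. In Section 9.4, apply the 80% and 2/3 benchmarks and their confidence bounds to MC sessions only, and word the Section 3 failure criteria to match. Restate the Section 9.2 precision on about 90 sampled MC sessions, or about 76 after attrition. Use Control scores on the MC tool for differentiation only.
2. Take session length from the existing recordings. Report contact minutes per session and per participant by arm, and interpret the exploratory Aim 3 estimate in that light.
3. Have the existing raters complete a short present/absent checklist of the Control elements in Section 6.1.1: graded practice, accuracy feedback, therapist-selected activity and assigned home practice. Label it neutrally and use it on all sampled tapes from both arms. A form used only on Control tapes would reveal the arm and hint at the hypothesis, against Sections 6.3 and 8.1. Report Control delivery descriptively, without a pass mark.

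The cost is a few extra rating minutes on about 180 tapes and wider stated bounds. The trial may also have to report an imperfect or unequal comparator. Participants do nothing more, and the design does not change.

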9.2 SAMPLE SIZE DETERMINATION

We will enroll 30 participants per group ($N = 60$). Although not required for an R21 proposal, we provide power analyses for our feasibility and fidelity hypotheses (Aims 1 & 2) assuming 15% attrition (see Table). We also estimate power for our (exploratory) pre-post comparisons of treatment effect (Aim 3). Based on our preliminary data (Goal Attainment $\Delta M = 2.4$, $SD = 0.97$), with $n = 30$ per group we will be able to detect mean differences in change of 0.85 in Attainment (2-tailed, $\alpha = 0.05$, 90% power). However, we want to reiterate that our reason for measuring treatment effect in this study is not to demonstrate efficacy but to obtain effect size estimates to power an efficacy trial. Our proposed sample size will provide enough information to achieve our aims and is feasible to accomplish in the timeframe of an R21.

Confidence bounds around target thresholds assuming 15% attrition (for Aim 2) and 95% confidence level.		
Aim	Outcome (with preliminary data source reference)	Target (Lower, upper)
1	Recruitment and retention	85% (73 – 93)
2a	Adherence (n=153 observations) ⁶¹	80% (78 - 82)

2a	Proficiency (n=153 observations) ⁶¹	3 (2.9 – 3.1)
2b	Acceptance: CSQ ⁵³	24 (23.8 – 24.2)
2b	Receipt: PRPS ⁷⁸	4 (3.8 – 4.2)
2b	Enactment: Homework completion ⁵³	80% (75 – 85)

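### The session-level t-test on Proficiency, and the session-level bounds for adherence and proficiency, ignore clustering by participant and therapist and so overstate precision

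*Combined protocol and SAP*

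**What the plan says.** Section 8.1 sets the rating sample: "The raters will rate a random sample (30%, n = 180) of MC and Control session audiofiles", spread so that it is "evenly distributed across condition, OT, treatment session number, and study month". Participant is not among the balancing factors.

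Section 9.4 uses these ratings in three ways. Adherence and proficiency are calculated for each therapist and held against benchmarks. For the outcomes as a whole, "For the Aim 2 outcomes, we will calculate mean scores" with 95% bounds and compare them with thresholds. For treatment differentiation, "we will compare Proficiency scores for the MC and Control sessions using" t-tests.

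The table in Section 9.2 is headed "Confidence bounds around target thresholds assuming 15% attrition (for Aim 2) and 95% confidence level". Its row "Proficiency (n=153 observations" has bounds of plus or minus 0.1, and the adherence row, on the same count, has plus or minus 2 percentage points. No SD, ICC or design effect is given.

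Section 6.3 says that, on assignment, the therapists of the relevant arm are told that a participant has joined their group. It also expects raters to work out which therapist gives which treatment. The number of therapists is not stated.

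**The concern.** A t-test on session scores treats every rated session as an independent observation. Proficiency scores a therapist's behaviour with a particular client, so two sessions from one therapist, or from one participant, would be expected to resemble each other. Participants sit within arms and, as Section 6.3 indicates, so do therapists. Positive correlation at either level therefore adds to the variance of the arm difference, and the session-level formula leaves that out.

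Nothing elsewhere repairs this. The correlation structures in Section 9.4 belong to the Aim 3 Goal Attainment model, and the per-therapist summaries serve the benchmarks, not the t-test. By contrast, Section 8.1 averages the participation ratings to one score per participant.

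Aim 2 is a primary objective and therapist fidelity a primary outcome. At stake are the p-value for differentiation and the width of the bounds around mean adherence and proficiency.

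**Working it through.** **The plan's own counts.** "We will enroll 30 participants per group" gives 60 participants, and "A complete intervention is defined as completion of 10 OT sessions" gives 10 sessions each.

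- Sessions: 60 × 10 = 600. Rated: 600 × 0.30 = 180. After 15% attrition: 180 × 0.85 = 153. Both stated counts reproduce, which confirms the session as the unit.
- Rated sessions per participant: 180 / 60 = 3 on average.
- Rated sessions per arm after attrition: 153 / 2 = 76.5.

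**The stated bound.** With no SD given, the proficiency bound can only be inverted. Setting 1.96 × SD / √153 = 0.1 gives SD = 0.63 (0.32 to 0.95 allowing for rounding of the bound). That inversion contains no design effect.

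**Effect of clustering.** With k therapists per arm,

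DE = 1 + (3 − 1) × ρ_participant + (76.5/k − 1) × ρ_therapist.

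The standard error is understated by √DE, and the true error of a nominal 5% test is 2 × [1 − Φ(1.96/√DE)]. The ICCs and k are assumptions.

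| ρ_participant | ρ_therapist | k | DE | √DE | True error |
|---|---|---|---|---|---|
| 0 | 0 | any | 1.0 | 1.00 | 5% |
| 0.1 | 0 | any | 1.2 | 1.10 | 7% |
| 0.2 | 0 | any | 1.4 | 1.18 | 10% |
| 0.4 | 0 | any | 1.8 | 1.34 | 14% |
| 0.1 | 0.01 | 2 | 1.57 | 1.25 | 12% |
| 0.1 | 0.05 | 3 | 2.43 | 1.56 | 21% |
| 0.1 | 0.05 | 2 | 3.06 | 1.75 | 26% |
| 0.1 | 0.10 | 2 | 4.93 | 2.22 | 38% |
| 0.4 | 0.10 | 2 | 5.53 | 2.35 | 40% |

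For example, in the sixth row, 1 + 2 × 0.1 + (25.5 − 1) × 0.05 = 2.43. Simulation with about 25 participants per arm and three sessions each agrees: about 7% at participant ICC 0.1, up to about 15% at 0.4, and about 20% to 40% once therapist ICC is 0.05 to 0.10.

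**Width for the arm difference** (SD 0.63). The session-level half-width is 1.96 × 0.63 × √(2/76.5) = 0.20. With ρ_participant 0.1, ρ_therapist 0.05 and k = 3 it is 0.20 × 1.56 = 0.31, or 0.44 on t with 4 degrees of freedom. With k = 2 it is 0.35, or 0.77 on 2 degrees of freedom.

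**Width for the Aim 2 means.** For the same sessions per therapist, the same √DE applies to the Section 9.2 bounds. Multiplying by 1.1 to 2.4, the proficiency half-width of 0.1 becomes 0.11 to 0.24, and the adherence half-width of 2 points becomes 2.2 to 4.8 points, before any allowance for few degrees of freedom.

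**Candidate remedies** (simulated false-positive rate, k = 2, ρ_participant 0.1, ρ_therapist 0.05): sessions 27%, participant means 21%, therapist means 5%. Averaging to participants is enough only when there is no therapist effect.

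**The case against.** The strongest reply is that the false-positive rate describes a situation the design makes implausible. Control leaves out strategies, metacognition, mediation and action plans (Section 6.1.1), and the scale gives 0 to an MC component that did not occur, while the MC benchmark is 2. A 1-point gap with SD 0.63 is still about 4.4 standard errors at DE 4.9. This largely stands. It is weaker with two therapists per arm, where the critical t value on 2 degrees of freedom is 4.3. A reader might infer that the plan could declare the treatments different when they are not; the documents make that unlikely.

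A reader might also infer that the proficiency difference and its interval feed the design of the definitive trial. The documents do not say so: Section 9.4 carries forward Goal Attainment effect sizes. It plans no interval for the proficiency difference and attaches no alpha, power or decision rule to this test. The Aim 2 failure criteria in Section 3 rest on averages and include none for differentiation.

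The larger inflation figures depend on an assumed therapist ICC and therapist number. If inference were limited to this pilot's own therapists, they could be treated as fixed, leaving only the participant-level factor of about 1.1 to 1.35. That position is defensible, but the plan does not take it, and even then the session-level test is not correct unless the participant ICC is zero.

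**Conclusion.** The point holds for precision. As written, the differentiation t-test and the session-level bounds for adherence and proficiency understate the standard error for any positive within-participant or within-therapist correlation. Confidence is high for the direction and limited for the size, which rests on the assumed ICCs, on two or three therapists per arm where a therapist effect is included, on an average of three rated sessions per participant, and on the reading of Section 6.3 that each therapist serves one arm. Under those assumptions the understatement is about 1.1 to 1.35 times from participants alone and about 1.6 to 2.4 times with therapists added.

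It does not follow that the differentiation conclusion would reverse. The p-value, and the Aim 2 bounds set against thresholds, are what would mislead. The change is worth making because it is cheap and Aim 2 is a primary objective.

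**What to change.** In Section 9.4:

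- Replace the session-level t-test with a linear mixed model of session proficiency on arm, with random intercepts for participant and therapist and small-sample degrees of freedom (for example Kenward-Roger).
- If the model does not converge, compare therapist means, not participant means.
- Compute the adherence and proficiency means and their 95% bounds with the same clustering.
- State the number of therapists per arm. If an arm has only one, report differentiation descriptively, because no model can separate arm from therapist.

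In Section 9.2, either label the adherence and proficiency bounds as assuming independent sessions or restate them with a design effect and the ICCs assumed.

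The cost is a few sentences and wider intervals, possibly much wider with few therapists. No new data are needed.
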